### *Visit 2 (procedure 1)– Randomization and Study Intervention*

STU#:

Eligible participants will return to the Lavin 14th floor Pain clinic within 2 weeks of the initial visit. Participants will be randomized to treatment or sham group. Participant pre-procedure 1 NRS pain score will be collected. Individual pain log will start 15 minutes after procedure. Participant will log pain score every hour until asleep. The next day, participant will record daily NRS pain score for 5 days.

Randomization

A computer-generated 1:1 block randomization scheme (<https://www.randomizer.org>) will be used to assign participants to receive a peri-sciatic nerve injection with either 10 mL of 2% lidocaine or 10 mL of preservative-free saline (compounded by the 11th floor Lavin pharmacy and labeled with a “1” or “2” to ensure adequate blinding). Randomization will be performed by a research assistant by opening an opaque envelope to reveal the participant number and group assignment printed inside of the envelope. This will instruct authorized study personnel to draw up either 2% lidocaine or saline (labeled “1” or “2” by compounding pharmacy per above). The blinded injectionist will be provided an unlabeled syringe of injectate immediately before the injection procedure. Participants, injectionist, and study personnel who collect outcomes data will be blinded to group assignment.

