## POWER ANALYSIS

Power and sample size calculations for this clinical trial were performed based on the data from a small cross-over study (N = 8) by Casale et al. The primary outcome variable will be achievability of  $\geq 50\%$  pain relief (dichotomous variable with yes/no), calculated from pre- and post-inject NRS in each of the lidocaine and sham conditions (i.e., pre-injection NRS – post-injection NRS). Based on the data from Casale et al., along with our expected, overall success rate of 75% by lidocaine injection, we calculated the difference in two proportions of discordant pairs to be 0.625 and the overall proportion of discordant pairs to be 0.875. Using these values and binomial enumeration (1,500 enumerations), along with an

STU#:

alpha level of 0.05, a power of 0.80, a two-sided t-test, and a dropout rate of 10%, the sample size was estimated as 20.

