#### STATISTICAL PLAN

Data for the primary outcome variable, proportion of participants reporting  $\geq 50\%$  immediate pain reduction from baseline, will be reported as the mean and standard deviation (or median and interquartile range if not normally distributed) of the lidocaine and sham groups. Mean change in pain score, will be examined using an unpaired t test (NCSS) (or Mann-Whitney U test if not normally distributed). The median difference and its 95% CI will be calculated. The criterion for rejection of the null hypothesis will be  $P < 0.05$ .

Participant data and secondary variables that are characterized by nominal data will be summarized as the number of participants in each category and the percentage of all participants in the group that they represent. These variables will be compared between the groups using the Pearson  $\chi^2$  test, or when at least one of the cells of the contingency table had an expected number less than five, the Fischer exact probability test. The Miettinen-Nurminen score will be used to calculate 95% CIs for differences in percentages where indicated.

Variables that are characterized by ordinal data and non-normally distributed continuous data (e.g., procedure time) will be summarized as median and interquartile range. These variables will be compared between the groups using the Mann-Whitney U test. Median differences and their 95% CIs will be calculated where indicated.

Variables that are characterized by normally distributed continuous data (e.g., age and body weight) will be summarized as mean and standard deviation. These variables will be compared between the groups using the unpaired t test (NCSS). Mean differences and their 95% CIs will be determined.

In case there were significant differences in the demographic variables, multivariate logistic and linear regression analyzes will be conducted to examine the binary and continuous outcome variables by group, while accounting for the statistically significant demographic variables analysis will be used to determine if any demographic or clinical variables (age, BMI, duration of pain, etc.) are independently associated with successful pain (NRS) outcomes.

Lastly, Pearson's correlation coefficients will be computed to assess the relationships among various demographic and procedural covariates.

STU#:

STU#:

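### No lidocaine-versus-saline comparison in the STATISTICAL PLAN includes a period term, although injection order is randomised; this mainly puts the continuous outcomes at risk

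*Combined protocol and SAP*

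**What the plan says.** The Randomization paragraph under Visit 2 uses "A computer-generated 1:1 block randomization scheme". Visit 3 then crosses both groups over, so what is randomised is the order of lidocaine and saline.

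The POWER ANALYSIS treats the primary endpoint as paired and takes "the difference in two proportions of discordant pairs to be 0.625 and the overall proportion of discordant pairs to be 0.875". Order does not enter that calculation.

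The STATISTICAL PLAN names an unpaired t or Mann-Whitney test for change in pain and a chi-square or Fisher test for nominal data. If demographic variables differ, "multivariate logistic and linear regression analyzes will be conducted to examine the binary and continuous outcome variables by group", adjusting for those variables. None of these has a term for period, sequence or participant.

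Item 5 of the Secondary Outcomes lists a general linear model for an interaction involving crossover sequence. It names neither the second factor nor the outcome. The STATISTICAL PLAN never mentions it, and nothing says that it adjusts the lidocaine-versus-saline comparison.

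**The concern.** In a two-period crossover, a systematic difference between the first and second injection is added to the lidocaine-minus-saline difference in one order and subtracted from it in the other. Pooling the orders turns that difference into extra error. If completers are unequal by order, it also shifts the estimate.

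Moving from unpaired to paired tests does not cure this, because an ordinary paired t test or McNemar test also pools the orders. The outcomes exposed are the continuous secondaries: NRS change at eleven time points, daily steps, OPUS and GARS.

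The schedule offers some routes to a period difference. Participants have no experience of the procedure at the first injection but do at the second. As written, OPUS is taken at Visit 1, up to two weeks before procedure 1, but at Visit 3 itself before procedure 2, so its change scores start from baselines of different age.

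**Working it through.** **Inputs from the POWER ANALYSIS.** These are "alpha level of 0.05, a power of 0.80, a two-sided t-test"; "a dropout rate of 10%, the sample size was estimated as 20"; a discordant difference of 0.625 and a discordant total of 0.875; and an "expected, overall success rate of 75% by lidocaine injection".

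**Assumptions, not in the documents.** The size of the period shift; completers by order; and a continuous treatment effect of 0.7 SD of the within-person difference, which gives about 80% power at 18 completers.

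**1. Reproduce the stated sample size.**
- Lidocaine-only responders: (0.875 + 0.625)/2 = 0.75. Saline-only responders: (0.875 − 0.625)/2 = 0.125.
- Exact two-sided McNemar power is 0.790 at n = 17 and 0.830 at n = 18. Then 18/0.9 = 20, as stated.
- The sample size therefore rests on a paired comparison that ignores order.

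**2. Effect of a period shift.** Let τ be the treatment effect, π the second-period minus first-period shift, s the SD of the within-person difference, and n1 and n2 the lidocaine-first and saline-first completers.
- Expected lidocaine-minus-saline difference: τ − π in lidocaine-first, τ + π in saline-first.
- Pooled, balanced orders: the mean is τ, but the variance rises from s² to about s² + π².
- Pooled, unequal orders: bias = −π(n1 − n2)/(n1 + n2).
- Average of the two order-specific means: τ whatever π is, with standard error (s/2)√(1/n1 + 1/n2) on n1 + n2 − 2 degrees of freedom.

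**3. Continuous outcomes, 9/9 completers, τ = 0.7, s = 1.** With a period term the noncentrality is 0.7 × √18 = 2.97 on 16 df, giving power 0.796. Without one and with no shift, it is 0.799 on 17 df. By simulation:

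| Assumed shift (SD) | Variance ratio 1 + π² | Paired t | With period term |
|---|---|---|---|
| 0 | 1.00 | 0.80 | 0.80 |
| 0.25 | 1.06 | 0.78 | 0.80 |
| 0.5 | 1.25 | 0.72 | 0.80 |
| 1 | 2.00 | 0.49 | 0.80 |

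**4. Bias.** At 10/8 completers it is 2/18 = 11% of the shift; at 10/6 it is 4/16 = 25%. For an assumed 20-point shift on the primary, that is 2.2 and 5 points against a planned difference of 62.5.

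**5. Binary primary at the plan's own cells.** The shift moves participants between the two discordant cells in opposite directions in the two orders.

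| Completers | Assumed shift (points) | Exact McNemar | Exact Prescott |
|---|---|---|---|
| 9/9 | 0 | 0.830 | 0.816 |
| 9/9 | 10 | 0.832 | 0.829 |
| 9/9 | 20 | 0.839 | 0.863 |
| 10/8 | 0 | 0.830 | 0.832 |
| 10/10 | 0 | 0.879 | 0.853 |

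With balanced orders the expected pooled discordant counts do not change, so McNemar loses nothing. At 10/8 with a 20-point shift favouring the second injection and more lidocaine-first completers, McNemar falls to about 0.80 through the bias in step 4; the Mainland-Gart test gives about 0.85.

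**The case against.** The strongest objection is that the unpaired analysis is the larger defect and hides this one. With the planned unpaired t test and an assumed within-person correlation of 0.5, power for a 0.7 SD effect is about 0.54 with no shift and 0.51 at a shift of 0.5 SD. A full crossover model adopted to repair the pairing would deal with period too. That stands, and the two belong in one edit. But a repair that only substitutes paired tests leaves the loss shown in step 3.

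A reader might also infer four stronger things, none of which the documents support.

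- *That the plan has no order-related model at all.* Item 5 exists. In this design a treatment-by-sequence interaction is the same contrast as the period effect, so item 5, once completed, may estimate it. What is missing is its completion and its link to the treatment comparison.
- *That the primary endpoint loses power.* At the plan's own inputs with balanced orders it does not. A loss appears under other assumptions: with independent response rates of 60% and 20%, 9/9 completers and a 30-point fall, McNemar goes from 0.553 to 0.502 and Prescott gives 0.599. At 10 points the same setting gives 0.547 against 0.559.
- *That a period difference is likely.* No document gives its size. Regression to the mean after entry on NRS above 4 is blunted, because response is measured from a fresh pre-injection NRS at each procedure.
- *That the result will be materially biased.* Blocked 1:1 allocation and about two expected dropouts make a large imbalance unlikely.

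**Conclusion.** The point holds as an omission in the specification. No lidocaine-versus-saline comparison is specified with a period term, and the only order-related model is incomplete and absent from the STATISTICAL PLAN.

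The cost falls on the continuous outcomes: from about 0.80 power to 0.72 at a 0.5 SD shift and 0.49 at 1 SD, given 18 completers, a 0.7 SD effect and a paired analysis. Bias is 11% of the shift at 10/8 completers. These sizes are conditional on assumed shifts, because the documents give none. For the binary primary, an order-based test is a reasonable choice and not a necessity. The stated sample size of 20 is unaffected.

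**What to change.** - **Continuous outcomes (STATISTICAL PLAN).** Analyse NRS change, steps, OPUS and GARS within participant, with treatment and period (first or second injection) as fixed effects and participant as a random or matched factor.
- **Secondary Outcomes, item 5.** Complete the sentence so that it is this model, and carry it into the STATISTICAL PLAN.
- **Binary primary.** Report the lidocaine-minus-saline difference as the average of the two order-specific differences, with a 95% CI. Pre-specify an exact order-based test (Prescott or Mainland-Gart) as either the primary or a supporting analysis.
- **POWER ANALYSIS.** If the order-based test is made primary, restate power for it. For Prescott this is about 0.82 at 9/9 completers, 0.83 at 10/8 and 0.85 at 10/10.

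**Cost.** Wording only, with data already to be collected and no change to the sample size. The continuous analyses give up one degree of freedom (0.796 against 0.799 with no shift). If Prescott replaces exact McNemar and there is no period effect, primary power falls by 0.830 − 0.816 = 1.4 points at 9/9 and by 0.879 − 0.853 = 2.6 points on these rounded figures at 10/10 (2.7 unrounded). Both remain above the stated 0.80.

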### Secondary Outcomes (between and within-group comparisons will be used for each outcome):

- 1) Mean and standard deviation (SD) of change in NRS pain score at 1, 2, 3, 4, 5, 6, 24, 48, 72, 96, 120 hours post-saline and lidocaine injections
- 2) Mean and SD of average daily steps recorded at 24, 48, 72, 96, 120 hours post-saline and lidocaine injections (via Modus StepWatchTM or Evolution EvoWalkTM)

STU#:

- 3) Mean and SD of change in Orthotics and Prosthetics User's Survey (OPUS) score immediately post-injection and conclusion of washout (5 days) in saline and lidocaine groups
- 4) Mean and SD of change in Groningen Activity Restriction Scale (GARS) score immediately post-injection and conclusion of washout (5 days) in saline and lidocaine groups
- 5) General linear model analysis of the interaction between crossover sequence
- 6) Demographic factors associated with large improvement in NRS pain score
- 7) Complications associated with the procedures

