Treatment block of sciatic nerve in contralateral limb: Procedure planning will be based on the participant’s indication of residual limb point of maximal pain (measured by distance from posterior superior iliac spine (PSIS) to most painful point [in cm]). Note that this point may beyond the anatomic end of the residual limb. The block will be performed at the exact same distance from PSIS on the contralateral side. If the block cannot be performed at this site due to anatomic or technical considerations (such as proximity to vascular structures), a more cephalad site along the sciatic nerve course will be selected for the procedure. During the block procedure, the participant will be positioned prone. Standard American Society of Anesthesiologists (ASA) procedure monitoring will be used (pulse oximetry, ECG, blood pressure, and heart rate). The participant’s skin will be prepared with chlorhexidine. A sterile ultrasound probe will be placed on the participants’ residual limb at a transverse angle in order to view the nerve in short-axis. The skin will be anesthetized with 1-2 mL of 1.0% lidocaine. The ultrasound probe (in plane) will be advanced to the intact limb’s sciatic nerve equidistance to that of the residual limb point of maximal pain. A 22-gauge standard echogenic needle will be placed adjacent to the sciatic nerve with ultrasound guidance. At the site of the nerve, 10mL of 2% lidocaine will be injected through the needle in the intervention group and 10ml of saline will be injected in the sham group.

In treatment group: At the site of the nerve, 10mL of 2% lidocaine will be injected through the needle

In control group: At the site of the nerve, 10ml of saline will be injected through the needle

Following injection, participants will be kept in recovery area and monitored for 30 minutes. They will also complete a pain log starting 15 minutes post-injection. After the first pain score is recorded, the participants will dress and exit procedure area. Participants will be required to arrange transportation as the block may impair lower extremity motor function.

Both saline and local anesthetic will be administered to all subjects with a crossover design as described above. Participants will undergo 5-day washout between injections.

*Visit 3 – Crossover for both groups*

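### The regressions for person-level predictors name no unit of analysis and no participant term in a crossover, so their error rate is uncontrolled if both results per person enter as separate rows

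*Combined protocol and SAP*

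**What the plan says.** The design is a two-period crossover with 1:1 allocation: "Both saline and local anesthetic will be administered to all subjects with a crossover design as described above" (Visit 2, Randomization and Study Intervention). Item 6 of the Secondary Outcomes is "Demographic factors associated with large improvement in NRS pain score", listed without any condition.

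The only method given for it is one sentence in the STATISTICAL PLAN. If demographic variables differ significantly, "multivariate logistic and linear regression analyzes will be conducted to examine the binary and continuous outcome variables by group", with adjustment for those variables. The sentence then runs, without a clean break, into a second purpose: finding which demographic or clinical variables "are independently associated with successful pain (NRS) outcomes". Age, BMI and duration of pain are the examples.

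No participant effect, clustered variance, GEE, mixed model or conditional model is named, and no number of rows per person is stated. The general linear model in item 5 of the Secondary Outcomes names no participant term either. The other group comparisons in the STATISTICAL PLAN are all for independent samples: unpaired t, Mann-Whitney, chi-square and Fisher.

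**The concern.** Age, BMI and pain duration belong to the person, not to the injection. If a regression contains treatment condition as a term and both results per person as separate rows, each covariate value appears twice. The software then computes its standard error as if there were 40 independent people (2 x 20), or 36 with 18 completers.

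That standard error is right only if a person's two responses are uncorrelated. With positive correlation, chance associations are reported as predictors too often. With negative correlation, real predictors are missed. Changing only the lidocaine-versus-saline test to a paired one would not cure this, because the covariate coefficients are estimated in a different model.

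At stake are the P values and confidence intervals for secondary outcome 6. The primary comparison is not affected by this point.

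**Working it through.** **1. The plan's own figure.** The POWER ANALYSIS states: "we calculated the difference in two proportions of discordant pairs to be 0.625 and the overall proportion of discordant pairs to be 0.875". Write p10 for success on lidocaine only and p01 for success on saline only.

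- p10 + p01 = 0.875 and p10 - p01 = 0.625, so p10 = 0.75 and p01 = 0.125.
- An exact two-sided McNemar calculation gives power 0.790 at n = 17 and 0.830 at n = 18. Then 18/0.90 = 20, which matches "alpha level of 0.05, a power of 0.80, a two-sided t-test, and a dropout rate of 10%, the sample size was estimated as 20".
- The asymptotic paired formula gives 15 (17 with dropout), the one-sided exact test 14 (16 with dropout), and an unpaired comparison 9 per group (12 with continuity correction). Of these, only the paired exact calculation gives 20, so the trial was sized on paired data.

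**2. Implied within-person correlation for binary success.** The plan also uses "our expected, overall success rate of 75% by lidocaine injection".

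- Success on both: 0.75 - 0.75 = 0. Saline success rate: 0 + 0.125 = 0.125. Success on neither: 1 - 0.875 = 0.125.
- phi = (0 - 0.75 x 0.125) / sqrt(0.75 x 0.25 x 0.125 x 0.875) = -0.09375 / 0.1432 = -0.65.
- At these success rates phi is largest when every saline responder also responds to lidocaine: (0.125 - 0.09375) / 0.1432 = 0.22.

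**3. Error rate of the unlinked analysis.** With two rows per person and correlation rho, the true variance of a person-level coefficient is (1 + rho) times the variance the model reports. The actual error of a nominal 5% test is therefore about 2 x [1 - Phi(1.96 / sqrt(1 + rho))].

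**4. Continuous NRS change.** The documents give no rho, so this is an assumed range. The simulation used ordinary least squares with a group term, 18 or 20 participants, 1 or 3 null covariates and 8,000 runs per setting.

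| rho | Formula | Simulation |
|---|---|---|
| -0.3 | 1.9% | 1.9-2.5% |
| 0 | 5.0% | 4.5-5.2% |
| 0.2 | 7.4% | 7.0-7.9% |
| 0.3 | 8.6% | 8.1-9.2% |
| 0.5 | 11.0% | 11.1-11.7% |
| 0.7 | 13.3% | 12.7-15.4% |

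The ceiling by formula, at rho = 1, is 16.6%. With one record per participant (data generated at rho = 0.5) the test returns to 4.7-5.0%.

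**5. Binary success.** Logistic regression with a group term and one null covariate, 18 or 20 participants, 3,000 runs per setting. The formula is approximate here because the two conditions have different variances.

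- Planning table (phi = -0.65): 0.1% by formula; simulated 0.2% (Wald) and 0.8-0.9% (likelihood ratio).
- Largest phi at the planned rates (0.22): 7.6% by formula; simulated 4-5% (Wald) and 8-9% (likelihood ratio). Part of the likelihood-ratio excess is small-sample error: with independent responses at the same rates it already gives 5.5-7.3%.
- An error rate near 10% on the Wald test (9-10%) appears only when the two success rates are closer than planned, for example 0.5/0.5 or 0.5/0.3 with phi = 0.5.

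**The case against.** The strongest case against has four parts.

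- **Two rows per person is not stated.** A reader might infer that the plan definitely counts 20 people as 40. It does not say so. The predictor clause looks like a second sentence run into the first. It could describe a separate analysis of the lidocaine response alone, with one row per person, and then the problem does not arise. This stands, and the point is conditional for that reason. The two-row reading remains the most natural one: the STATISTICAL PLAN's groups are lidocaine and sham, a model of outcomes by those groups needs both results, and the neighbouring tests treat the groups as different people.
- **The size is not the plan's.** A reader might also infer that false positives run at about twice the nominal rate. That needs a continuous outcome and rho of roughly 0.4-0.6, which the documents do not supply. For successful pain outcomes, which the predictor clause names and the plan defines as a yes/no variable, the planning inputs point the other way. This stands too. It does not rescue the plan, since a test running below 1% has little chance of finding a real predictor.
- **The regression may never run.** It depends on significant demographic differences. If the groups are the two conditions, the same people are in both, and with complete data their demographics are identical. If the groups are the two sequences, the data layout is different again. This stands, and it leaves the unconditional secondary outcome 6 without a clear method.
- **It shares a cause with the unpaired treatment tests.** True, and one statement that the participant is the unit of analysis could cover both. The consequence for covariates is different and needs its own sentence.

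**Conclusion.** The gap is real. The plan specifies neither the unit of analysis nor any participant term for person-level predictors, in a trial where everyone contributes two results. If both results enter as unlinked rows, a nominal 5% test of a predictor runs at about 7-13% for continuous NRS change with assumed rho of 0.2-0.7, and below 5% with negative rho. For binary success it runs under 1% at the plan's own inputs. The planned success rates cap phi at 0.22, or about 7.6% by formula.

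The conclusion rests on the two-row reading and, for NRS change, on an assumed correlation. The phi of -0.65 is a consequence of the planning inputs, not an observed value. The documents do not support a general claim of doubled error. What they support is that the error rate is uncontrolled and its direction unknown. The effect is confined to the regression-based secondary results.

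**What to change.** In the STATISTICAL PLAN:

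1. Separate the predictor analysis for secondary outcome 6 from the conditional sentence on demographic differences. State it as its own analysis and name its outcome.
2. Test person-level predictors with one record per participant. The lidocaine response asks who does well after the block; the lidocaine-minus-saline difference asks in whom the block adds most. Say which is meant.
3. If both results are kept, link them. For continuous outcomes use a linear mixed model with a participant random intercept and small-sample degrees of freedom (for example Kenward-Roger). For binary success use GEE logistic regression clustered on participant with a small-sample variance correction. A random intercept constrained to non-negative variance cannot represent a negative correlation, so allow a compound-symmetric residual covariance if that is possible.
4. State that the effective sample for predictors is the number of participants, not of injections.

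The cost is SAP wording and a different model call, with no new data or participants. The downside is wider intervals for predictors when the correlation is positive: relative to the unlinked analysis, by a factor of about sqrt(1 + rho), for example sqrt(1.5) = 1.22 at rho = 0.5.
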